Arm 2: Exemestane 25 mg/ 3 times a week (3 active tablets and 4 placebo tablets)

Arm 3: Exemestane 25 mg/once a week (1 active tablet and 6 placebo tablets)

Treatment start (day 1)

The participant starts treatment, a telephone contact will be performed only if different from the randomization day

Telephone contact (a week before surgery +3 days)

Review of self-reported compliance, concomitant medications, toxicity assessment.

Final clinical visit (the day of surgery or the day before)

Physical exam, toxicity assessment, concomitant medications, blood collection for clinical lab tests and circulating biomarkers, compliance/review pill diary. The blood withdrawn for biomarkers will be at 12 hours, 1.5-2.5 days and 5.5-6.5 days from last active dose respectively for arm 1, 2 and 3 depending on scheduled final visit. Participants continue intervention until the night before surgery

Surgery (4 to 6 weeks; ideally at day 29)

Surgery performed; Surgical specimens collected

* After identifying the pool of 180 potentially eligible women with ER-positive in-situ or invasive breast cancer, women in Italy and the U.S. undergo identical procedures. Specifically, consent for blood draw, laboratory testing, completion of questionnaire, etc. -as outlined under baseline clinic visit- will be performed.

Endpoints

Primary endpoint: Percentage change in time of serum estradiol concentration at alternative dosing schedules compared to daily dose.

Secondary endpoints: Safety and toxicity, change in Ki-67 and PgR expression, tissue estradiol, exemestane and 17-dihydroxyexemestane concentration.

Circulating estrogens (including ultrasensitive estradiol measurement), androgens and sex hormone binding globulin, exemestane and 17-dihydroxyexemestane, adipokines, glucose, insulin and lipid profile. Further secondary endpoints will be proteomics and UGT2B17 genotype and measurement of crown-like structures in non-cancerous breast fat tissue.

TABLE OF CONTENTS

COVER PAGE.....	1
SCHEMA.....	7
1. OBJECTIVES.....	10
1.1 Primary Objective.....	10
1.2 Secondary Objectives.....	10
2. BACKGROUND.....	10
2.1 Breast Cancer.....	10
2.2 Exemestane.....	10
2.3 Rationale.....	11
3. SUMMARY OF STUDY PLAN.....	14
4. PARTICIPANT SELECTION.....	15
4.1 Inclusion Criteria.....	15
4.2 Exclusion Criteria.....	15
4.3 Inclusion of Women and Minorities.....	16
4.4 Recruitment and Retention Plan.....	16
5. AGENT ADMINISTRATION.....	16
5.1 Dose Regimen and Dose Groups.....	16

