1. OBJECTIVES

1.1 Primary Objective

It has been shown that exemestane reduces estradiol levels both at the standard dose (25 mg/day) and at lower doses. We expect to achieve with 25 mg three times a week and 25 mg/week similar effects in estradiol reductions to the standard dose of 25 mg daily.

Non-inferiority of percent change in time of serum estradiol levels, adjusted for baseline levels, following four up to six weeks of exemestane 25 mg given three times per week or one time per week compared with exemestane 25 mg daily dosing.

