5.2 Exemestane Administration

Investigational drug pharmacy will be responsible for drug distribution. [name] (PI) and the local Site Investigators or their designees will be responsible for drug administration. They can delegate to other study investigators (MDs and research nurses) to distribute the agent on their behalf.

Participants will receive a 6-week supply (2 wallets containing 3 blisters each) of the drug/placebo as outlined in the clinical procedure schema (see Section 7.1 for a detailed description). Each wallet will consist of 3 blisters, each blister for 7 days of treatment. Each blister will have 7 tablets numbered from 1 to 7 to clearly mark the order to be taken by the participants. Based on the arm, the blister will contain 7 active tablets 1 through 7, or three active tablets corresponding to days 1, 3 and 5 and four placebo tablets at days 2, 4, 6 and 7, or one active tablet placed at day 1 and 6 placebo in the remaining 6 days. The participant will be advised to take one tablet per day after dinner, always at approximately 8 PM, starting from day 1 till the night before surgery. If for any reason they will skip a tablet they will be instructed to leave it behind and take the one for the corresponding day. Participants will be asked to contact the study coordinator the first time they miss a dose.

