7. CLINICAL EVALUATIONS AND PROCEDURES

7.1 Schedule of Events

The possibility of taking part in a pre-surgical trial will be presented to incoming postmenopausal women with a highly suspicious palpable lesion or a newly diagnosed ER-positive DCIS or breast cancer. The baseline visit will be scheduled for interested potential participants after histological confirmation.

SCHEDULE OF EVENTS

Evaluation/ Procedure	Screening Visit ¹	Baseline Visit/ Registration (within 14 days prior to randomization)	Randomization	Phone call (Day 1)	Phone call (1 week +3 days prior to surgery) ²	Final Visit (Days 28+1, 35+1, or 42+1) ³	Surgery (Days 29, 36 or 43) ¹²
Screening Informed Consent	X						
Tru-cut biopsy (Eligibility ER + breast cancer)	X						
Informed Consent		X					
Assess eligibility		X					
Medical history		X					
Physical exam/ height/weight/vital signs		X				X ^{9,10}	
Tobacco / alcohol use assessment		X					
Fasting blood lab tests ⁴		X				X	
Blood lab tests that may not be fasting ⁵		X				X ¹⁰	
Fasting blood for biomarkers ⁶		X				X	
Tissue for biomarkers (FFPE blocks or slides)		X					X
Frozen tissue for biomarkers							X
Frozen tissue for proteomics ¹¹							X ¹¹
Concomitant medications		X			X	X	
Baseline symptoms		X					
Confirm eligibility		(X)	X				
Randomization			X				
Dispense study agent ¹³			X ¹³				
Treatment initiation				X ⁷			
Collect study agent						X	X
Compliance					X	X	
Review agent diary/record						X	
Adverse events					X	X	
QoL questionnaire ⁸		X				X	

¹ For the Italian sites only

² If the participant is seen on site for the physical exam and blood safety tests on Day 7 prior to surgery, perform all procedures in person rather than as a phone call. In all other cases call the participant on the phone 1 week +3 days prior to surgery

³ Based on institutional procedure, the final visit may occur on the same day as surgery or the day before. The Final Visit must be

conducted on Days 28+1, 35+1, or 42+1.

⁴ **Fasting** blood lab tests (local lab): Glucose, total cholesterol, HDL cholesterol and triglycerides. Fasting is strongly recommended, but is not mandated. Every effort should be taken to draw these labs fasting.

⁵ Blood tests for safety that do not require fasting: complete blood count (CBC), AST, ALT, Na, K, BUN, total bilirubin, Cl, Ca, alkaline phosphatase, creatinine, and FSH if needed

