7.5 Evaluation at Completion of Study Intervention

At the final visit, participants will undergo physical exam, vital signs, and anthropometric measurements (weight, waist measurement, hip measurement). These procedures may be done **within 7 days prior to surgery or on the day of surgery**. Do not repeat the height assessment at the Final Visit. Height measurement will be used from the baseline visit.

Blood tests for safety that do not require fasting may be done **within 7 days prior to surgery or on the day of surgery**:

- complete blood count (CBC), AST, ALT, Na, K, BUN, total bilirubin, Cl, Ca, alkaline phosphatase, and creatinine

All other procedures are performed the day of surgery or the day before surgery:

Fasting blood lab tests that are performed at the local lab (glucose, total cholesterol, HDL cholesterol and triglycerides). Fasting is strongly recommended, but is not mandated. Every effort should be taken to draw these labs fasting.

Fasting blood for biomarkers will be collected. Fasting is strongly recommended, but is not mandated. Every effort should be taken to draw these labs fasting.

The date and time of blood draw, the date and time of surgery, and the date and time of last pill intake will be recorded.

The use of concomitant medications, adverse events, compliance, and quality of life assessment will be assessed. Study agent will be collected. A review of agent diary will be performed.

Any kind of surgery will be allowed from simple lumpectomy to total mastectomy. Tissue samples will be collected from the surgical specimen and processed according to Section 10. A detailed Manual of Operations and Procedures will be implemented with the specific procedures for each specimen.

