13.4 Primary Objective, Endpoint(s), Analysis Plan

Primary objective and primary endpoint

Since the primary objective of this study is to assess if the reduction in estradiol with the standard dose is comparable with the other lower doses, we will measure the estradiol before and after treatment. Thus, the primary endpoint is the percentage change of serum estradiol concentration from baseline and we will compare the median change and percentage changes among arms.

We choose the percentage change as the primary endpoint because it will improve generalization of results, given the wide variability among different assays, and because we predict that a large percentage of participants will have the final values of estradiol below the detectable level.

Analysis plan

We will present full distribution and median values of estradiol at baseline (before treatment), at post (after treatment), and changes and percentage changes (with interquartile ranges) of estradiol level, from baseline to post, by arms. Differences by arms of % change, change and final values will be tested considering t-test and ANCOVA models. Estradiol at baseline will be included as explanatory variable together with other possible confounders such as BMI, age and time since last dose. Normal distribution of residuals from full model will be checked and, if needed, a transformation will be considered.

We will also compare percentages of participants with final values of estradiol below the detectable level by arms with Chi-square tests and logistic models.

We will carry out the two comparisons with the standard dose considering $\alpha=0.025$.

Power analysis

Given the expected reduction of at least 80% change with exemestane at 25 mg daily (56) considered as reference group (control arm) against 25 mg 3 times a week, or 25 mg weekly, for the power calculation we assume a non-inferiority difference of 6% in percentage changes of estradiol after treatment from baseline, using a one-sided, two-sample t-test. A total sample size of 162 participants (54 participants per arm), enables us to achieve 80% power with a margin of equivalence of -6% in the mean percentage changes from baseline at the lower dose compared to the standard dose. The true difference between the means percentage changes is assumed to be 0.0%.

The significance level of the test is 0.025 to take into account of multiple comparisons (we will compare the changes at the two low doses with the standard dose)(57).

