13.6 Reporting and Exclusions

The primary analysis will employ an intention-to-treat approach, which includes all women irrespective of compliance. An according-to-protocol subgroup analysis will be restricted to women who are “compliant”, such as participants who have taken $\geq 80\%$ of the active scheduled pills, and notably, due to the different arm schedule, $\geq 80\%$ of the active pills has to be reached also in the last 7 days before surgery.

Due to limitations of estradiol analysis procedures, small concentrations cannot be precisely measured. These concentrations are said to be below the limit of detection (LOD). We will consider a statistical method that uses the characteristics of the distribution of the values above the LOD to estimate the values below the LOD. This can be done with an extrapolation technique or maximum likelihood estimation that has smaller error rates than all the standard replacement techniques (Methods of Dealing with Values Below the Limit of Detection using SAS. Croghan et al.).

Patterns of observations for covariates will be classified as complete cases (no missingness), terminal (monotone) dropouts, intermittent (non-monotone) dropouts, mixed and no-data. Kendall’s τ_b will be computed in order to test the correlation between a dichotomous indicator of missing observations and treatment assigned as well as any possible baseline covariates.

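### The primary-endpoint ANCOVA lists time since last dose as a confounder; if that means last active dose, the randomised schedule sets it and it should not be adjusted for

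*Combined protocol and SAP*

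**What the plan says.** Section 13.4 gives two kinds of model for the primary endpoint: "Differences by arms of % change, change and final values will be tested considering t-test and ANCOVA models". On covariates it says: "Estradiol at baseline will be included as explanatory variable together with other possible confounders such as BMI, age and time since last dose". It does not say whether the dose in question is the last active tablet or the last tablet of either kind, and it does not say which model decides non-inferiority.

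Other sections bear on the meaning:

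- The Schema (final clinical visit) sets the biomarker draw at "12 hours, 1.5-2.5 days and 5.5-6.5 days from last active dose respectively for arm 1, 2 and 3".
- Section 5.2 fixes the blister layout. Arm 2 has active tablets on days 1, 3 and 5. Arm 3 has "one active tablet placed at day 1 and 6 placebo in the remaining 6 days". Section 7.3 has treatment end on the seventh blister day. Together these produce the Schema's intervals.
- Section 7.5 requires that "the date and time of last pill intake will be recorded", and that pill may be a placebo.
- Section 7.1, footnote 3: "Based on institutional procedure, the final visit may occur on the same day as surgery or the day before".
- Section 13.6 defines the primary analysis as one that "includes all women irrespective of compliance".
- Section 1.1 states the objective as "Non-inferiority of percent change in time of serum estradiol levels, adjusted for baseline levels".

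**The concern.** BMI, age and baseline estradiol are fixed before randomisation. Time since last active dose is not: it follows from the allocated schedule. A variable determined by allocation cannot confound the comparison of allocations. It is one of the ways in which the regimens differ.

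Section 1.1 asks whether one regimen is non-inferior to another. An ANCOVA that conditions on time since active dose asks how the arms would compare at the same interval from an active tablet, which the planned schedules never produce. If estradiol recovers between doses, the adjustment credits that recovery to the covariate and removes it from the arm effect. The variation left within arms is not randomised either. It comes from the draw day, which follows local practice, and from missed tablets.

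Two things are at stake: loss of power when the schedules are truly equivalent, and a false claim of non-inferiority when the less frequent schedule falls short because suppression wears off. The t-test is unaffected. However, section 1.1 asks for baseline adjustment, which the t-test does not provide, so the ANCOVA could well be the result reported. If the two disagree, the plan has no rule for which one counts.

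**Working it through.** **Inputs from section 13.4:** margin 6 points, common SD 11, one-sided alpha 0.025, true difference 0, 54 evaluable per arm. **From the Schema:** draw times after the last active dose. A draw the day before surgery falls at 1.5 days (arm 2) or 5.5 days (arm 3). A draw on the day of surgery falls at 2.5 or 6.5 days. Arm 1 is at 0.5 days either way. **Assumed:** the split of draws between the two days, adherence, and the shape and slope of any recovery.

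**1. The plan's own figure.** SE = 11 × √(2/54) = 2.12. The non-centrality is 6/2.12 = 2.83, and the non-central t on 106 df gives power 80.2%. With 10% drop-out, 54/0.9 = 60 per arm. The plan's numbers reproduce, for a t-test without covariates.

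**2. Adding time since last active dose.** In a three-arm model with time as a linear covariate,

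SE² = 11² × [2/54 + Δ²/W],

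where Δ is the difference in mean time from arm 1 and W is the pooled within-arm sum of squares of time.

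*Half the draws the day before, full adherence.* Mean times are 0.5, 2.0 and 6.0 days, so Δ = 1.5 and 5.5. W = 2 × 54 × 0.25 = 27, and the slope SE is 11/√27 = 2.12.
- Three times weekly: 2.12 × √(1 + 1.5²) = 3.8; power about 35%.
- Weekly: 2.12 × √(1 + 5.5²) = 11.8; power about 7%.

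*20% of draws the day before, full adherence.* Δ = 1.8 and 5.8; W = 2 × 54 × 0.16 = 17.28; slope SE 2.65.
- Three times weekly: √(2.12² + (1.8 × 2.65)²) = 5.2; power about 21%.
- Weekly: √(2.12² + (5.8 × 2.65)²) = 15.5; power about 6%.

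If every draw fell at one fixed time per arm, W would be zero and the arm effect could not be estimated.

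**3. Missed tablets.** Missed active doses widen the within-arm spread and restore some precision. The simulation assumed doses missed independently and draws between 8 and 10 AM. Power (three times weekly / weekly) was:

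| Active doses missed | Half the day before | 20% the day before |
|---|---|---|
| 2% | about 52% / 13% | about 42% / 11% |
| 5% | about 65% / 20% | about 59% / 18% |
| 10% | about 72% / 30% | about 69% / 27% |

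**4. Draw day fixed by site.** With centre in the model, two of five near-equal sites drawing the day before, and full adherence, the SEs are 6.3 and 20.9. With 5% missed they are 2.6 and 5.7.

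**5. Bias.** If percentage change worsens linearly by b points per day since the last active dose, adjustment removes b × Δ from the arm contrast. At the 50:50 split:

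| b (points/day) | Three times weekly | Weekly |
|---|---|---|
| 0 | 0 | 0 |
| 0.25 | 0.4 | 1.4 |
| 0.5 | 0.75 | 2.75 |
| 1 | 1.5 | 5.5 |

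**6. False non-inferiority, weekly arm.** Let the true deficit be 6 points, all of it linear recovery. At full adherence b = 6/5.5 = 1.1 (50:50) or 6/5.8 = 1.0 (20% the day before). Without the covariate the error rate is the nominal 2.5%. With it, the adjusted contrast averages zero, so the claim rate equals the power at zero difference: about 6-7% at full adherence. In simulation it was about 11-13% with 2% missed, 19-21% with 5% and 26-32% with 10%.

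**The case against.** The strongest counter-argument is textual. Where the protocol means active tablets it usually says so, as in the Schema and sections 5.7 and 13.6. Section 13.4 does not, and section 7.5 records the last pill. On that reading every woman is at a similar interval and the covariate is close to harmless. The list of confounders is also illustrative, and the margin and power are tied to a two-sample t-test, which this covariate does not touch. These points stand. They make the finding conditional and mean the plan is not committed to the damaging model. They do not remove the problem, because the term is undefined, the Schema times this same draw from the active dose, and no deciding analysis is named.

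The second objection is to the figures. Draw split, adherence and linear recovery are assumed. Section 2.2 cites suppression lasting no less than five days after a single dose, which does not support steady recovery from 12 hours. It also does not rule out recovery at the weekly arm's 5.5-6.5 days. Normal errors with SD 11 ignore the detection floor that the plan itself expects. The power loss and the false-claim rate belong to different truths and do not add up. All of this is fair: the figures show the mechanism and its possible size, and are not a forecast for this trial.

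Finally, wanting to account for the one-day spread in draw time is legitimate. That spread does not depend on arm, though, and can be studied within arms.

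**Conclusion.** The concern holds, conditional on the active-dose reading. On that reading the covariate is a consequence of treatment, and adjusting the arm comparison for it changes the question asked in section 1.1. The loss of precision at full adherence depends only on the Schema's times, the plan's sample size and SD, and the draw split: the SE rises from 2.12 to about 4-5 points for three times weekly and 12-15 points for weekly. Missed doses recover precision but make false claims more frequent. The bias is zero if estradiol does not recover between doses. If it does, the bias favours the less frequent schedules, and more so the weekly one. The t-test result is safe either way. This should be fixed before analysis, since the correction costs nothing under either reading.

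**What to change.** In section 13.4:

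- Remove time since last dose from every between-arm model of the primary endpoint, and state that no variable measured after randomisation enters those models.
- Name one deciding analysis for each comparison with daily dosing: ANCOVA of percentage change on arm, with baseline estradiol, centre, BMI stratum and age as covariates. This matches section 1.1 and the stratification in section 13.2. Keep the t-test as supportive.
- Define time since last active dose from the diary, blister position and recorded draw time. Report it by arm, and explore its relation to estradiol within arms 2 and 3 only.

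The cost is two or three sentences. No new data, visits or participants are needed.

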The data are drawn from populations with common standard deviations of 11% (58).

Assuming a 10% drop-out rate while on study, we would need to randomize 180 participants (60 participants per arm) to achieve the total sample size of 162 evaluable participants (54 participants per arm).

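### Holm at the overall one-sided 0.05 that section 13.4 implies would raise power for both schedules from 69% to 79% with no extra patients: a cheap improvement, not an error in the plan

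*Combined protocol and SAP*

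**What the plan says.** The power analysis in section 13.4 of the combined protocol and SAP works "using a one-sided, two-sample t-test" and claims 80% power "with a margin of equivalence of -6% in the mean percentage changes from baseline at the lower dose compared to the standard dose". On the level it says: "The significance level of the test is 0.025 to take into account of multiple comparisons". The parenthesis that follows names the comparisons: "we will compare the changes at the two low doses with the standard dose". The analysis plan in the same section repeats the level: "We will carry out the two comparisons with the standard dose considering" alpha of 0.025, this time without giving the sidedness.

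No ordering, step-down or joint procedure is given for the primary endpoint. The only other multiplicity method is Benjamini-Hochberg, for the secondary endpoints (section 13.5). The overall family-wise level is not written anywhere.

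Two further statements bear on any change. Section 13.8 promises 95% confidence intervals for every measure of response. Section 6.9 lists the statistician among those who are not blinded to schedule.

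**The concern.** The only reason offered for 0.025 is the number of comparisons, and 0.05 / 2 = 0.025. That is a Bonferroni split of an overall one-sided 0.05. The split holds the second test at 0.025 even after the first schedule has passed. Holm releases the full 0.05 for the remaining test at that point, and the overall error still cannot exceed 0.05, even though the two tests share the daily arm.

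Suppose one schedule passes at 0.025 and the other has a p-value between 0.025 and 0.05. The plan leaves the second schedule unproven, although the overall level it implies would allow the claim. Section 1.1 expects both schedules to perform like daily dosing, so this outcome is relevant.

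**Working it through.** **Inputs (all from section 13.4).** Margin 6 percentage points. Standard deviation: "The data are drawn from populations with common standard deviations of 11" percent. True difference: "The true difference between the means percentage changes is assumed to be 0.0" percent. One-sided 0.025 per test, 54 evaluable per arm, 10% drop-out.

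**1. The plan's own figure.** The normal formula is n = 2 (z₀.₉₇₅ + z₀.₈₀)² SD² / margin².

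2 × (1.960 + 0.842)² × 121 / 36 = 52.8, so 53 per arm.

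The noncentral t gives power 0.794 at 53 and 0.802 at 54, so 54 is the smallest adequate size. Evaluable total 3 × 54 = 162, and 162 / 0.90 = 180 randomized. The plan's figures reproduce.

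**2. Plain split at 54 per arm.** The standard error of a difference is 11 × √(2/54) = 2.117, and 6 / 2.117 = 2.834. The shared daily arm gives the two test statistics a correlation of 0.5.

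- Normal approximation: Φ(2.834 − 1.960) = 0.809 per schedule, and 0.700 for both (bivariate normal).
- Simulated pairwise t-tests, 2,000,000 trials per scenario: 0.802 per schedule and 0.690 for both.
- At least one: 0.802 + 0.802 − 0.690 = 0.914.

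**3. Holm at 54 per arm.** Write c₁ for the critical value at 0.025 and c₂ for that at 0.05. With equal true differences,

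P(both) = 2 P(T₁ > c₁, T₂ > c₂) − P(T₁ > c₁, T₂ > c₁).

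This gives 0.797 by the normal approximation and 0.791 by simulation. The first step is the same as in the split, so P(at least one) stays at 0.914. Per schedule: (0.914 + 0.791) / 2 = 0.853.

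**4. Other truths (simulation, %).** Losses are percentage points worse than daily dosing.

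| True losses | Quantity | Plain split | Holm |
|---|---|---|---|
| 0 and 0 | each schedule | 80.2 | 85.3 |
| 0 and 0 | both | 69.0 | 79.1 |
| 0 and 0 | at least one | 91.4 | 91.4 |
| 0 and 2 | the worse schedule | 46.5 | 57.0 |
| 0 and 2 | both | 42.8 | 55.2 |
| 2 and 2 | both | 29.9 | 41.1 |
| 0 and 6 | false claim | 2.5 | 4.9 |
| 6 and 6 | any false claim | 4.6 | 4.6 |

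For the last row the bivariate normal gives 4.5 for either method.

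**5. The gain expressed as patients.** Under the plain split, the normal approximation for both schedules gives 0.794 at 65 per arm and 0.802 at 66. About 66 evaluable per arm would therefore be needed to match Holm's 0.797 at 54. That is 198 evaluable, or 198 / 0.90 = 220 randomized instead of 180.

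**6. If the intended overall level were one-sided 0.025.** Each test would need 0.0125. Power per comparison at 54 per arm would then be 71%, and the normal formula would ask for 64 per arm for 80%.

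**The case against.** The plan's choice is legitimate. Two tests at 0.025 control the error, and Bonferroni is an accepted conservative option. That stands.

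A reader might infer that 69% power for both schedules means the trial is underpowered. The documents do not support this. Section 13.4 claims 80% for each comparison, section 1.1 joins the two schedules with an or, and no passage promises joint power. The chance of showing at least one schedule is 91% either way.

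A reader might also infer that Holm has the same error rate and so costs nothing. Only the ceiling is the same. If one schedule matches daily dosing and the other sits exactly at the margin, which is a plausible outcome for a dose-reduction trial, the false claim becomes about twice as likely (2.5% to 4.9%).

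Four further limits stand:

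- The overall 0.05 is inferred. The alternative, an overall one-sided 0.025, would leave the plan with no multiplicity allowance and contradict its stated reason, but the sponsor has to confirm.
- One-sided 0.025 matches the 95% intervals of section 13.8. Under Holm, a second schedule could pass while its 95% interval crosses the margin.
- Holm ranks two p-values. Section 13.4 lists t-tests and ANCOVA for percentage change, change and final values, with a possible transformation, so one primary test per schedule has to be named first.
- The document is already at Version 11, Amendment 3, and the statistician is unblinded. A late change to the success rule could look data-driven unless its timing is documented.

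The power figures also assume normal data, while section 13.4 expects many final values below detection. The size of the gain under that distribution was not calculated.

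**Conclusion.** This is a cheap improvement to a valid plan. Taking the overall level as one-sided 0.05, Holm never rejects less than the split. Under the plan's inputs it adds 5 points of power per schedule (80% to 85%) and 10 points for both (69% to 79%), and nothing for at least one. If one schedule is truly 2 points worse, its power rises from 47% to 57%.

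The family-wise error stays within 5%, but more of that allowance is used when only one schedule is inferior.

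The result rests on the inferred overall level, normal data, SD 11 and margin 6. It does not show that the sample size, the 80% statement or the error control in section 13.4 is wrong.

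**What to change.** Confirm the intended overall level. If it is one-sided 0.05, replace the sentence on the significance level in section 13.4, and align the matching analysis-plan sentence, along these lines:

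*The family-wise level for the primary endpoint is one-sided 0.05. The two non-inferiority tests on percentage change in serum estradiol, each lower-dose schedule against daily dosing, use the Holm procedure: the smaller p-value is tested at 0.025 and, if significant, the other at 0.05. The Holm decision governs the conclusion. The 95% intervals are reported for both comparisons, together with the 90% interval for a decision made at the second step.*

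Name the single test that supplies each p-value. Because the statistician is unblinded (section 6.9), date and document the change before any estradiol results by arm are seen. Keep 162 evaluable, 180 randomized and the 80% per-comparison statement.

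The cost is a few lines of text, with no added patients, visits or assays. The downside is that a second-step claim rests on a 90% rather than a 95% two-sided interval. If the intended overall level was one-sided 0.025, do not make this change.
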